7.13.2 Quality Assurance of Study

The sponsor assures the quality of the study by establishing an audit department that is independent of the department that implements the study. In order to assure the quality of the study, the personnel in charge of audit performs audit at appropriate timing at the sponsor as well as at study sites and other facilities involved in the study as necessary, in accordance with the standard operating procedures of the sponsor.

7.14 ETHICAL IMPLEMENTATION OF STUDY

7.14.1 Review of Study

This study is reviewed by the institutional review board (IRB)/EC selected by each study site as to whether or not its implementation is appropriate from the perspective of ethical, scientific, and medical adequacy.

7.14.2 Continued Review of Study

The adequacy of continued implementation of this study at a particular study site is reviewed once a year or more frequently, or in the following cases.

- 1) When the sponsor notified the Principal Investigator of serious and unexpected ADRs or other events
- 2) When the Principal Investigator reported serious AEs or other events
- 3) When the Principal Investigator reported a revision of consent form and other written information for patients
- 4) When the Principal Investigator submitted the overview of the current status of the study for the review regarding continuation of the study
- 5) Other cases in which the Principal Investigator considers that the review regarding continuation of the study is necessary

The Principal Investigator requests the opinion of the institutional review board (IRB)/EC regarding the adequacy of continuation of the study at the study site concerned.

7.14.3 Matters Related to Protection of Privacy and Personal Information of Participants

In order to protect the privacy and personal information of participants, participants are identified by subject IDs.

In the preparation and handling of case report forms and the monitoring, audit, and other tasks performed by the sponsor, as well as when the study results are published, attention is paid to protection of privacy and personal information of participants.

7.15 STORAGE OF RECORD

7.15.1 Investigator

Essential documents should be retained until at least 2 years after the last approval of a marketing application in an ICH region and until there are no pending or contemplated marketing applications in an ICH region or at least 2 years have elapsed since the formal discontinuation of clinical development of the investigational product. These documents should be retained for a longer period, however, if required by the applicable regulatory requirements or by an agreement with the sponsor.

7.15.2 Institutional Review Board (IRB)/EC

The institutional review board (IRB) /EC is an independent body constituted of medical, scientific and non- scientific member, whose responsibility is to ensure safeguard the rights, safety, and well-being of all trial participants.

The institutional review board (IRB) /EC should retain all relevant records (e.g., written procedures, membership lists, lists of occupations/affiliations of members, submitted documents, minutes of meetings, and correspondence) for a period of at least 3 years after

completion of the trial and make them available upon request from the regulatory authority(ies).

7.15.3 Sponsor

- 1) The sponsor specific essential documents should be retained until at least 2 years after the last approval of a marketing application in an ICH region and until there are no pending or contemplated marketing applications in an ICH region or at least 2 years have elapsed since the formal discontinuation of clinical development of the investigational product. These documents should be retained for a longer period however if required by the applicable regulatory requirement(s) or if needed by the sponsor.
- 2) When the storage of the documents that should be stored by the Principal Investigator or the institutional review board (IRB) /EC becomes unnecessary, the sponsor notifies the institutional review board (IRB) /EC to that effect through Investigator.

7.16 MONETARY PAYMENT

The sponsor pays the cost of this study based on the contract with each study site.

7.17 INSURANCE

The sponsor takes necessary measures including issued guarantee letter in order to compensate for the treatment of health hazards of participants caused by the study and other losses.

7.18 COMPENSATION FOR HEALTH HAZARDS

- 1) When any health hazard occurs to a subject in this study, the study site and the sponsor respond to it for the subject or his or her bereaved family in the following manner.
- 2) The study site makes all possible efforts to treat the health hazard.
- 3) If neither intention nor negligence of the sponsor was involved and no other parties have liability for the health hazard caused by the study, the sponsor provides compensation based on its compensation system. However, if the health hazard was proven to be the results of the subject's own intention or significant negligence, the compensation is reduced or not provided. If a health hazard that newly occurred is causally unrelated to the study, it is not compensated.
- 4) If intention or negligence of the sponsor, the study site, a party commissioned by the sponsor or the study site to carry out study-related tasks, or other parties was involved in the health hazard caused by the study, the party that is legally responsible for this health hazard provides the compensation.
- 5) Adverse event that happened during observation and treatment period will be monitored by investigator and sponsor. The cost for the adverse event related to the study will be compensated by sponsor.

15. Leaflet Pirofel. Indonesia

Appendix 1

FORMULIR PEMERIKSAAN

[figure not shown]
Jenis Formulir	Diisi oleh
Formulir 2, Inventerisasi Rasa Nyeri Singkat	Pasien
Formulir 3, Pemeriksaan Awal Nyeri Pasien	Dokter Pemeriksa
Formulir 4, Pemeriksaan Indikator Rasa Nyeri Non – Verbal	Dokter Pemeriksa
Formulir 5, Pemeriksaan Rentang Gerak	Dokter Pemeriksa
Formulir 6, Pemeriksaan Kekuatan Otot	Dokter Pemeriksa
Formulir 7, Pemberian aplikasi obat topikal	Fisioterapis
Formulir 8, Sensasi Termal	Pasien
Formulir 9, Program Fisioterapi & Latihan	Fisioterapis

FORMULIR PASIEN**FORMULIR PEMERIKSAAN 2**

[figure not shown]
INVENTERISASI RASA NYERI SINGKAT		
Nama	:	
Tanggal	:	
Waktu	:	
Kunjungan ke	:	

**Isilah pertanyaan dibawah ini sesuai dengan kondisi yang Anda rasakan hari ini.
Lingkari yang paling mendekati kondisi Anda.**

[figure not shown]
1	
Sepanjang hidup kita, kebanyakan dari kita mengalami rasa sakit dari waktu ke waktu (seperti sakit kepala ringan, terkilir, dan sakit gigi).
 
Pernahkah Anda merasakan sakit selain rasa sakit biasa tersebut hari ini?
	:	
Ya
 
Tidak

2	
Pada diagram, arsir area di mana Anda merasakan sakit. Beri tanda X pada area yang sangat sakit
		

- 3** Nilai rasa sakit Anda dengan melingkari salah satu angka yang sangat menggambarkan rasa sakit Anda yang TERBURUK di 24 jam terakhir.

- 4** Nilai rasa sakit Anda dengan melingkari salah satu angka yang sangat menggambarkan rasa sakit Anda yang PALING RINGAN di 24 jam terakhir

5	Nilai rasa sakit Anda dengan melingkari salah satu angka yang sangat menggambarkan rasa sakit Anda RATA-RATA.		
	
 <hr/> 0 1 2 3 4 5 6 7 8 9 10 
 
 
 Tidak ada rasa sakit 
 
 Rasa sakitnya luar biasa seperti yang bisa Anda bayangkan 
 
		
6	Nilai rasa sakit Anda dengan melingkari salah satu angka yang menggambarkan rasa sakit yang sedang Anda rasakan SEKARANG.		
	
 <hr/> 0 1 2 3 4 5 6 7 8 9 10 
 
 
 Tidak ada rasa sakit 
 
 Rasa sakitnya luar biasa seperti yang bisa Anda bayangkan 
 
		
7	Pengobatan atau perawatan apa yang Anda terima untuk rasa sakit Anda?	:	
8	Dalam 24 jam terakhir, seberapa banyak rasa sakit tersebut berkurang setelah menerima pengobatan atau perawatan? Lingkari salah satu persentase yang sangat menggambarkan RASA LEGA yang Anda rasakan.		
	
 <hr/> 0% 10% 20% 30% 40% 50% 60% 70% 80% 90% 100% 
 
 
 Tidak berkurang sama sekali 
 
 Sepenuhnya Hilang 
 
		
9	Lingkari salah satu angka yang menggambarkan bagaimana, selama 24 jam terakhir, rasa sakit mengganggu Anda dalam :		

A. Kegiatan sehari-hari:

0	1	2	3	4	5	6	7	8	9	10
Tidak mengganggu							Sangat mengganggu			

B. Suasana hati:

0	1	2	3	4	5	6	7	8	9	10
Tidak mengganggu							Sangat mengganggu			

C. Kemampuan berjalan:

0	1	2	3	4	5	6	7	8	9	10
Tidak mengganggu							Sangat mengganggu			

D. Pekerjaan biasa (termasuk bekerja di luar rumah dan pekerjaan rumah):

0	1	2	3	4	5	6	7	8	9	10
Tidak mengganggu							Sangat mengganggu			

E. Hubungan dengan orang lain:

[figure not shown]
0	1	2	3	4	5	6	7	8	9	10
Tidak mengganggu							Sangat mengganggu			

	
F. Tidur:
 
 <hr style="border: 0; border-top: 1px solid black; width: 100%;"/> 
 012345678910 
 
 
 Tidak mengganggu Sangat mengganggu 

	
G. Kesenangan hidup:
 
 <hr style="border: 0; border-top: 1px solid black; width: 100%;"/> 
 012345678910 
 
 
 Tidak mengganggu Sangat mengganggu 

Paraf Pasien: _____ **Tanggal :** _____

FORMULIR DOKTER PEMERIKSA

FORMULIR PEMERIKSAAN 3		
PEMERIKSAAN AWAL RASA NYERI		
Nama	:	
Tanggal	:	
Waktu	:	
Kunjungan ke	:	

1	
Lokasi rasa nyeri
 
2	
Pemeriksaan intensitas dan karakter rasa nyeri
 
1. Serangan dan pola sementara :
 
 • Kapan Anda mulai merasakan sakit? • Seberapa sering rasa sakit itu muncul? • Apakah ada perubahan dalam intensitasnya? 
2. Lokasi
 
 • Dimana Anda merasakan sakitnya? • Apakah dirasakan lebih dari satu titik? 
3. Keterangan
 
 • Bagaimana rasa sakit yang Anda rasakan? • Bagaimana cara Anda menjelaskan rasa sakit tersebut?

	
4. Intensitas
 
Dalam skala 0 hingga 10, dengan 0 berarti tidak sakit sama sekali dan 10 berarti rasa sakit terburuk yang dapat Anda bayangkan,
 
 • Berapa skalanya saat ini? • Berapa skalanya ketika Anda sedang merasa sangat kesakitan? • Berapa skalanya ketika Anda merasa sakitnya di saat terbaik? 
5. Faktor yang memperburuk dan meringankan –
 
 • Apa yang meringankan rasa nyeri Anda? • Apa yang memperburuk rasa nyeri Anda? 
6. Perawatan sebelumnya –
 
 • Jenis pengobatan apa yang pernah Anda lakukan untuk meringankan rasa nyeri Anda? • Apakah pengobatan itu efektif? 
7. Efek –
 
 • Bagaimana rasa nyeri tersebut mempengaruhi fungsi fisik dan sosial Anda?
3	
Pemeriksaan psikososial

4	
Pemeriksaan fisik dan neurologis

Paraf Dokter Pemeriksa : _____ **Tanggal :** _____

FORMULIR DOKTER PEMERIKSA

FORMULIR PEMERIKSAAN 4		
PEMERIKSAAN INDIKATOR RASA NYERI NON- VERBAL		
Nama	:	
Tanggal	:	
Waktu	:	
Kunjungan ke	:	

Penilaian:

- Beri nilai 0 jika perilakunya tidak teramati.
- Beri nilai 1 jika perilaku muncul secara singkat selama beraktivitas atau sedang beristirahat.

Jumlah angka indikasi dihitung untuk perilaku yang diamati :

- saat sedang beristirahat,
- dalam pergerakan, dan
- keseluruhan.

Tidak ada batas nilai yang jelas dalam mengindikasikan tingkat keparahan suatu rasa nyeri; sebaliknya, keberadaan perilaku apa pun dapat menjadi indikasi suatu rasa sakit, menjamin investigasi pengobatan, dan pengawasan lebih lanjut dari para praktisi

No	Perilaku	Saat beraktivitas	Saat beristirahat
1	Keluhan vocal: nonverbal (Menghela napas, terkesiap, erangan, menggeram, menangis)		
2	Ekspresi Wajah/Meringis (Alis berkerut, mata menyipit, gigi terkatup rapat, bibir mengatup, mulut menganga, ekspresi terdistorsi)		
3	Bersiap (Mencengkeram atau berpegangan pada mebel, perkakas, atau area yang terdampak selama bergerak)		
4	Gelisah (Terus atau sesekali berganti posisi, berayun, tangan bergerak sesekali atau terus menerus, tidak bisa diam)		

5	Menggosok (Memijat bagian yang terdampak)		
6	Keluhan vocal: verbal (Ucapan mengekspresikan ketidaknyamanan atau rasa sakit (misalnya; “aduh”, “sakit”); mengumpat saat bergerak; berseru atau protes [misalnya, “berhenti”, “cukup”])		
	Nilai total		

Paraf Dokter Pemeriksa : _____ **Tanggal :** _____

FORMULIR DOKTER PEMERIKSA

FORMULIR PEMERIKSAAN 5		
PEMERIKSAAN RENTANG GERAK		
Nama	:	
Tanggal	:	
Waktu	:	
Kunjungan ke	:	

S**O****A****P**
Paraf Dokter Pemeriksa : _____ **Tanggal :** _____

FORMULIR DOKTER PEMERIKSA

FORMULIR PEMERIKSAAN 6		
PEMERIKSAAN KEKUATAN OTOT		
Nama	:	
Tanggal	:	
Waktu	:	
Kunjungan ke	:	

S**O****A****P**

Paraf Dokter Pemeriksa : _____ **Tanggal :** _____

FORMULIR FISIOTERAPIS

PEMBERIAN OBAT TOPIKAL		
NOMOR OBAT TOPIKAL YANG DIBERIKAN :		
Nama	:	
Tanggal	:	
Waktu	:	
Kunjungan ke	:	
Lokasi area pengaplikasian obat topikal 
 
		
Sebelah Kiri / Kanan	:	

[figure not shown]
Paraf Fisioterapis : _____ **Tanggal :** _____

FORMULIR PASIEN**FORMULIR PEMERIKSAAN 7****PEMERIKSAAN SENSASI TERMAL (ASHRAE)**

Nama	:	
Tanggal	:	
Waktu	:	
Kunjungan ke	:	

Sensasi Termal

Mohon lingkari skala berikut yang sesuai dengan yang Anda rasakan setelah diaplikasikan obat topikal

Reference: M. Schweiker, M. André and F. Al-Atrash et al. / Energy & Buildings 211 (2020) 109761

[figure not shown]
Sensasi termal tersebut dirasakan dalam waktu :

_____ Menit

_____ Detik

Kenyamanan setelah aplikasi obat topikal

[figure not shown]
Mohon lingkari skala berikut yang sesuai dengan yang Anda rasakan setelah diaplikasikan obat topikal

Reference: M. Schweiker, M. André and F. Al-Atrash et al. / Energy & Buildings 211 (2020) 109761

Penerimaan sensasi termal yang diaplikasikan secara topikal

[figure not shown]
Mohon lingkari skala berikut yang sesuai dengan yang Anda rasakan setelah diaplikasikan obat topikal

M. Schweiker, M. André and F. Al-Atrash et al. / Energy & Buildings 211 (2020) 109761

Paraf Pasien : _____ Tanggal : _____

FORMULIR FISIOTERAPIS

PROGRAM FISIOTERAPI DAN LATIHAN		
Nama	:	
Tanggal	:	
Waktu	:	
Kunjungan ke	:	
Lokasi area nyeri 		
Sebelah Kiri / Kanan	:	
Program fisioterapi yang dilakukan	:	
Program latihan yang dilakukan	:	

Paraf Fisioterapis : _____ **Tanggal :** _____

Appendix 2

PROGRAM FISIOTERAPI STANDAR UNTUK PARTISIPAN

Diagnosis	OSTEOARTRITIS
Program Terapi & Latihan	Waktu Pengerjaan (menit)
Latihan Peregangan: Peregangan otot paha belakang, Peregangan otot betis, Peregangan otot paha depan Latihan Isometrik: Quadriceps isometris	Tahan selama 15 detik, dilakukan sebanyak 3 set Tahan selama 15 detik, dilakukan sebanyak 3 set
Terapi Manual: Pemijatan pada area otot yang kaku dan tegang	Dilakukan oleh Fisioterapi selama 10-15 menit
Terapi modalitas: TENS (Transcutaneous Electrical Nerve Stimulation) Penggunaan Ultrasound	Dilakukan selama 15 menit Dilakukan selama 10 menit
Terapi tambahan jika pasien datang dalam keadaan bengkok: Terapi Es, kompres	Dilakukan selama 15 menit

Diagnosis	ANKLE SPRAIN
Program Terapi & Latihan	Waktu Pengerjaan (menit)
Latihan Rentang Gerak: Mobilisasi anteroposterior sendi talokrural Latihan isometris: Dorsofleksi, plantarfleksi, inversi dan eversi menggunakan tahanan	10 repetisi, 3set Tahan 10 detik, 3set

Terapi Manual: Pemijatan pada area otot yang kaku dan tegang	Dilakukan oleh Fisioterapi selama 10-15 menit
Terapi modalitas: TENS (Transcutaneous Electrical Nerve Stimulation) Penggunaan Ultrasound	Dilakukan selama 15 menit Dilakukan selama 10 menit
Terapi tambahan jika pasien datang dalam keadaan bengkak: Terapi Es, kompres Ankle Pumping	Dilakukan selama 15 menit Dilakukan 10 repetisi, dilakukan sebanyak 3set

Diagnosis	TENDINITIS PATELLA
Program Terapi & Latihan	Waktu Pengerjaan (menit)
Latihan Fleksibilitas: Fleksibilitas flektor pinggul dan paha depan Mobilitas lumbosacral Latihan Isometrik: Quadriceps isometric Latihan Penguatan: Side Lying abduction, clam shell, hipe hike satu kaki	Dilakukan 3 set 15 repetisi Tahan 10 detik, dilakukan 3set Dilakukan 3 set 15 repetisi
Terapi Manual: Pemijatan pada area otot yang kaku dan tegang	Dilakukan oleh Fisioterapi selama 10-15 menit
Terapi modalitas: TENS (Transcutaneous Electrical Nerve Stimulation) Penggunaan Ultrasound	Dilakukan selama 15 menit Dilakukan selama 10 menit

Terapi tambahan jika pasien datang dalam keadaan bengkak:	
Terapi Es, kompres	Dilakukan selama 15 menit

Diagnosis	TENNIS ELBOW
Program Terapi & Latihan	Waktu Pengerjaan (menit)
Latihan Rentang Gerak: Rentang gerak sendi siku pasif dan aktif	Dilakukan 10-12 repetisi, 3set
Latihan Isometris: Flektor/ekstensor pergelangan tangan	Tahan 10 detik, dilakukan 3 set
Terapi manual: Pemijatan pada area otot yang kaku dan tegang	Dilakukan oleh Fisioterapi selama 10-15 menit
Terapi modalitas: TENS (Transcutaneous Electrical Nerve Stimulation) Penggunaan Ultrasound	Dilakukan selama 15 menit Dilakukan selama 10 menit
Terapi tambahan jika pasien datang dalam keadaan bengkak: Terapi Es, kompres	 Dilakukan selama 15 menit

Diagnosis	BACK PAIN
Program Terapi & Latihan	Waktu Pengerjaan (menit)
Latihan Isometris: Abdominal Isometrik	Tahan selama 10 detik, Dilakukan sebanyak 3 set
Latihan Peregangan: Knee to Chest (single & double), Pelvic Twist, Hamstring Bridge, Cat & Camel, Cobra & Childpose	Tahan selama 15 detik, dilakukan sebanyak 3 set

Terapi manual: Pemijatan pada area otot yang kaku dan tegang	Dilakukan oleh Fisioterapi selama 10-15 menit
Terapi modalitas: TENS (Transcutaneous Electrical Nerve Stimulation) Penggunaan Ultrasound	Dilakukan selama 15 menit Dilakukan selama 10 menit

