6.8.1 Test Drug : Counterpain® PXM

- Active Ingredients : Piroxicam plus Counterirritant (Methyl Salicylate, Eugenol and Menthol)
- Dose :
Adults : Refer to product's leaflet as follow: no occlusive dress should be employed. Apply gel to the affected area three times daily leaving no residual material on the skin. 1 gram of gel (~ 3 cm) applied to the affected area.

The affected areas are:

- The arms: hand, wrist, elbow, shoulder sinistra or dextra
- The legs: feet, ankle, knee sinistra or dextra
- Upper back or Lower back

3 times daily means:

- application one time in morning (06.00 – 11.00),
- one time in afternoon (11.01 – 17.00),
- one time in evening (17.01 – 23.00).

Application of gel will use dosing cards that provided in this clinical study.

- Method of administration: external use only.
- Every visit, participants will get 2 tubes and in total are 6 tubes for 6 ± 1 days application.

Justification:

The dosage for use refers to the Counterpain® PXM leaflet which has been approved by BPOM RI.

Refer to Counterpain® PXM data that 1 gram equal to 3 cm.

Counterpain PXM dalam gram	Setara dengan ukuran (cm)	Setara dengan assay Piroxicam (mg)	Kandungan zat Counterirritant didalamnya		
			Methyl Salicylate	Menthol	Eugenol
1 gram Counterpain PXM	3 cm	Mengandung Piroxicam 4.7 - 5.1 mg	Methyl Salicylate 97.2 - 119.17 mg	Menthol 48.5 - 55.9 mg	Eugenol 12.5 - 14.7 mg

1. 1 GRAM

[figure not shown]

Foto ukuran dalam cm yang setara dengan 1 gram Counterpain PXM

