7.9.1 Primary Endpoint

The assessment of primary endpoint will be assessed through form 2, Inventerisasi Rasa Nyeri Singkat on 1st Visit, 2nd Visit and 3rd Visit.

The primary end-point is the difference BPI scale ≥ 3 , from initial scale of pain to the end of treatment will be captured as the primary efficacy endpoint.

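### The Form 2 pain-intensity items name no body site while the gel is applied locally, so pain at untreated sites can attenuate arm differences and raise the risk of falsely declaring equivalence

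*Protocol*

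**What the plan says.** - **Source of the primary score.** Protocol 7.9.1: "The assessment of primary endpoint will be assessed through form 2, Inventerisasi Rasa Nyeri Singkat on 1st Visit, 2nd Visit and 3rd Visit". Neither 5.1, 7.9.1 nor 7.4.2 says which item, or combination of items, is the score.
- **Wording of the items.** In Appendix 1, Form 2, items 3 to 6 ask for worst, least, average and current pain. Item 3 asks for the number "menggambarkan rasa sakit Anda yang TERBURUK di 24 jam terakhir" (worst in the last 24 hours). Item 6 reads "Nilai rasa sakit Anda dengan melingkari salah satu angka yang menggambarkan rasa sakit yang sedang Anda rasakan SEKARANG" (pain now). None names a joint, a side or the treated area.
- **Body diagram.** Item 2 reads "Pada diagram, arsir area di mana Anda merasakan sakit. Beri tanda X pada area yang sangat sakit" (shade where it hurts, put an X where it hurts a lot). Items 3 to 6 do not refer back to it.
- **Treatment is local.** Section 6.8.1 has "1 gram of gel (~ 3 cm) applied to the affected area", with a list of regions such as "The arms: hand, wrist, elbow, shoulder sinistra or dextra" and "The legs: feet, ankle, knee sinistra or dextra". The topical application form has one location field and a left/right choice.
- **Other painful sites.** Sections 6.2 and 6.3 neither require a single painful site nor exclude pain elsewhere. Form 3 asks "Apakah dirasakan lebih dari satu titik" (is it felt at more than one point), but no rule follows from the answer.
- **Order on Day 0 (7.7.2).** Form 2 is step 3. Examination is step 4, diagnosis step 6, and randomisation with the application form step 7.
- **Analysis (7.4.2).** Pairwise TOST on mean change from baseline, margin ±1.0.

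**The concern.** The treatment acts where it is applied, but the outcome is not tied to that place. The target population in 6.1 includes osteoarthritis and back pain, and a participant may have a second painful knee, or a painful back as well as a painful knee. If that second site gets no gel, nothing on Form 2 tells the participant to leave it out of the rating.

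For the piroxicam 0.5% gel, section 2.1 puts plasma concentrations at about 5% of those after equivalent oral or intramuscular doses. The protocol therefore gives little reason to expect the gels to differ at a site they are not rubbed into. Scores set by such a site carry almost no information about the difference between gels.

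In a superiority trial this would cost power. In an equivalence trial it pulls the arms together and so works towards the trial's own claim. Randomisation balances untreated pain between arms in expectation, so no particular gel is favoured, but the attenuation remains. A participant whose treated site recovered can also miss the reduction of 3 points or more because another site still hurts.

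**Working it through.** **Inputs from the protocol.** SD 1.81, margin 1.0 and 54 per arm (6.7); TOST within ±1.0 (7.4.2). Section 6.7 uses α = 0.05/3 = 0.0167 per comparison, while 7.4.2 uses 0.05 unless adjusted, so both are shown.

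**The plan's own figure.** The 54 does not follow from the printed formula: (2.39 + 0.84) × 1.81 / 1.0 = 3.23 × 1.81 = 5.85, and 5.85² ≈ 34.2. The protocol prints 4.059 in place of 3.23, and (4.059 × 1.81)² = 54.0. I use 54 only as the planned evaluable number per arm (180 × 0.9 / 3 = 54). The present point does not depend on how it was derived.

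**Assumption.** The protocol gives no prevalence of multi-site pain. Let m be the share of participants whose score is set entirely by untreated pain, with no between-arm difference there. For a treated-site difference d, the expected observed difference is (1 − m) × d.

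**Formula (normal approximation, 1.81 taken as the SD of the change).**

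- SE = 1.81 × √(2/54) = 0.348
- Equivalence is declared when the estimate lies within ±c, where c = 1.0 − z × SE. At one-sided 0.05, c = 1.0 − 1.645 × 0.348 = 0.427.
- P(declare) = Φ((c − (1 − m)d)/SE) − Φ((−c − (1 − m)d)/SE)

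**Worked line.** With d = 1.0 and m = 0.2, (0.427 − 0.8)/0.348 = −1.07. The second term is negligible, so P = 14.2%.

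**Chance of falsely declaring equivalence, true treated-site difference exactly 1.0:**

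| m (assumed) | Expected difference | SD 1.81, one-sided 0.05 | SD 20% higher, one-sided 0.05 | SD 1.81, one-sided 0.0167 |
|---|---|---|---|---|
| 0 | 1.0 | 5.0% | – | 1.7% |
| 0.1 | 0.9 | 8.7% | 7.8% | 3.2% |
| 0.2 | 0.8 | 14.2% | 11.8% | 5.9% |
| 0.3 | 0.7 | 21.6% | 16.9% | 10.0% |

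**The opposite effect.** Untreated pain may also add between-patient variance, which makes equivalence harder to show. With no true difference and one-sided 0.05, power at 54 per arm falls from 78% to 55% if the SD rises by 20%.

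**A difference outside the margin.** Take d = 1.2. At m = 0.2 the expected difference is 0.96, and at m = 0.4 it is 0.72. Both are below 1.0, but the 90% confidence interval has half-width 1.645 × 0.348 = 0.57, so its expected upper limits are 1.53 and 1.29. The chance of declaring equivalence is about 6% and 20%, against 1.3% undiluted.

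**The case against.** **A true difference beyond the margin need not pass.** A reader might infer that a 1.2-point difference diluted to 0.96 or 0.72 would be called equivalent because it falls inside ±1.0. The protocol does not support that. TOST judges the confidence interval, and in these cases the trial would still fail to show equivalence about 94% and 80% of the time. What stands is that the risk is several times the undiluted one.

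**Full dilution is a worst case.** If the treated site is the worse one at baseline, the score still falls until the other site sets it, so dilution is partial. Untreated pain may also ease through natural recovery, physiotherapy or rescue paracetamol. This weakens any claim of fixed non-response. It does not restore a difference between gels at a site they do not reach.

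**The one-area limit is inferred.** A reader might take the singular wording and the left/right field to mean that gel may go on one area only. The protocol does not say so: 6.8.1 lists several regions, and 6.8.2 lets the amount follow the extent of the painful area. The point therefore applies only where another painful site is in fact untreated. Likewise, Form 3's question about several points is routine history-taking and does not show that such patients are expected in number.

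**Form 2 has some protection.** Item 1 sets aside everyday pains such as a mild headache or toothache, and the item 2 diagram could show a mismatch with the application site. So one cannot say that any new pain simply counts as failure of the gel. But a diagram identifies a mismatch without supplying a score for the treated site. Form 3's intensity questions name no site either, so no later analysis plan can recover one.

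**The primary item is undefined.** True, and a separate gap. The point holds for each of items 3 to 6. If the interference questions in item 9 entered the score, the fix below would not cover them.

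**Conclusion.** The point holds as a measurement weakness that should be corrected before enrolment. The pain-intensity items are not tied to the treated site, treatment is local, and eligibility does not address other painful sites. The direction is towards equivalence.

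The size cannot be taken from the protocol. With 10% to 30% of participants scoring untreated pain (assumed), the false-equivalence risk at the margin goes from 5% to about 9% to 22% at one-sided 0.05, or about 8% to 17% if the SD is 20% higher. At 0.0167 with the SD unchanged it goes from 1.7% to between 3.2% and 10.0%. These figures rest on full dilution within the affected share, so they are upper values for each share.

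A reader might conclude that the equivalence result would be invalid or that one gel is favoured. Neither follows: the loss is attenuation, partly offset by added variance that lowers power, and its extent depends on how many participants have a second, untreated painful site.

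**What to change.** 1. On Day 0, have the investigator name one index area for measurement, the area to be treated, before the baseline Form 2 is completed and before randomisation. Form 2 now precedes examination and diagnosis, and the application form is filled in only at step 7, so the order in 7.7.2 must change. Keep Form 2 in the same position relative to the examination at all three visits, because item 6 asks about current pain.
2. Carry the same area to the topical application form.
3. Add one instruction to Form 2 at all three visits, with the area written in: *Please answer questions 3 to 6 for this area only.*
4. State in 5.1 and 7.9.1 that the primary pain score refers to the index area, and name the item or items that form it.

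This concerns what is scored. Whether gel may be applied to more than one area is for the sponsor and investigators to state.

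Cost: a small change to the Day 0 order, one line on a patient form, two short text changes, and a small departure from the standard questionnaire wording. No extra visits or participants are needed.
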